The model based proportion of eyes with acceptable absolute rotation with its corresponding 95% confidence interval (CI) will be constructed for each lens type from the generalized linear mixed model. Acceptable absolute rotation will be concluded if the lower limit of the 95% CI is greater than or equal to 0.80 (80%).

Contact Lens Related Corneal Staining (CS) Analysis:

Each eye/subject will be categorized into two groups such that ‘response=1’ if an eye had acceptable corneal staining (CS) (i.e., CS grade 2 or lower) throughout all planned and unscheduled visits or ‘response=0’ otherwise. The incidence rate of the Test lens will be compared to the Control lens using a generalized linear mixed model with binomial distribution and logit link function. The model will include lens type as a fixed effect and site, subject and eyes nested within subject as random effects. Baseline characteristics such as age and gender may be considered as covariates in the model when appropriate.

The incidence rate of CS for the Test lens will be compared to the Control lens using the two-sided 95% CI constructed for odds ratios (Test over Control). No difference between Test and Control lenses will be concluded if the 95% CI of the odds ratio contains 1.

Monocular Visual Acuity (VA) 20/20 or better Analysis:

Observed monocular VA will be also dichotomized such that ‘response=1’ if VA was 20/20 or better (refer as ‘suitableVA’) or ‘response=0’ otherwise at fitting. Dichotomized VA at fitting will be compared between the Test and Control lenses using a generalized linear mixed model with binomial distribution and logit link function. The

model will include lens type as a fixed effect and site, subject and eyes nested within subject as random effects. Baseline characteristics such as age and gender may be considered as covariates in the model when appropriate.

The model based proportion of eyes with suitable VA at fitting will be compared between the Test and Control lenses using the two-sided 95% CI constructed for odds ratios (Test over Control). Non-inferiority will be concluded if the lower limit of the two-sided 95% CI of the odds ratio is above 0.4. The odds ratio margin of 0.4 corresponds to a 10% difference in proportion between the Test and Control lenses assuming a reference rate of 93%.

CLUE Score Analysis:

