The proportion of dichotomized acceptable absolute rotation (acceptable absolute rotation is defined as absolute rotation \leq 10-degree) at 15-minute post insertion (Visit 1) in the Atlas A group will be compared to a historical control proportion (p_0) of 80%. The alternative hypothesis is at least 80% of eyes in the Atlas A group will have acceptable absolute rotation at 15-minute post insertion whereas the null

hypothesis is less than 80% of eyes in the Atlas A group will have acceptable absolute rotation. The following hypothesis testing for proportion will be assessed:

$$H_0: p < p_0 \text{ vs. } H_a: p \geq p_0,$$

where p represents the population proportion and p_0 represents a historical control proportion of 80%.

Contact Lens Related Corneal Staining (CS)

The proportion of dichotomized unacceptable contact lens related CS (unacceptable CS is defined as CS grade 3 or higher) in the Atlas A group will be compared to the proportion of that in the AOA group throughout all planned and unplanned visits. The alternative hypothesis is the odds of unacceptable CS incidence rate in the Atlas A group ($OR_{Atlas A}$) is not statistically different from the odds of that in the AOA group (OR_{AOA}) throughout the wear period. The following hypothesis testing for odds ratio will be assessed:

$$H_0: OR = 1 \text{ vs. } H_a: OR \neq 1,$$

where OR represents the ratio of $OR_{Atlas A}$ over OR_{AOA} ($OR_{Atlas A}/OR_{AOA}$) and Ψ_0 represents a margin of 1 that reflects distribution similarity between the Atlas A and AOA groups.

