1.5. Sample Size Justification

Sample size was calculated to attain the optimal number of subjects to demonstrate the statistical acceptance of the primary and secondary hypotheses using the historical data from CR5699 and CR5799. The incidence rates (%) of the primary endpoints from the historical data are presented in Table 2 below.

Table 2: Incidence Rate (%) from the Historical Data

Endpoints	Event	Atlas A Rate (%)	AOA Rate (%)
Monocular Visual Acuity 20/40 or better	Overall	100	100
Monocular Visual Acuity 20/20 or better	Overall	93.2	92.9
Corneal Staining < Grade 3*	Overall	100	100
Acceptable Lens Fit	Fitting	100	100
Absolute Rotation within 10-degree	15-min	97	96
Stability with Blink within 5-degree	Fitting	100	100

*Corneal staining will be assessed to demonstrate no difference between the Atlas A and AOA lenses whereas the other primary endpoints will be assessed to demonstrate satisfying a minimum threshold (80%) of the Atlas A.

Primary Endpoints with a 80% Threshold:

The common reference rate of 95% was selected for the sample size calculation as all applicable primary endpoints are binary in nature. Assuming a correlation of 0.8 between eyes, 2000 trials (replicating 2000 trials) were simulated to attain a sample size with a minimum statistical power of 90%.

Primary Endpoints with No Difference:

The incidence reference rate of 0.005% was selected for the sample size calculation for no difference between two study lenses on corneal staining grade 3 or higher using the formula given by Diggle et al. (2002¹) for cluster binary data. The incidence rate of 0.005% was set considering the 5 previous Atlas studies (both sphere and astigmatism) including CR5417, CR5582, CR5726, CR5699 and CR5799. There were no incidences of corneal staining grade 3 or higher among all 5 studies, hence it was deemed that 0.005% is a reasonable incidence rate. The number of observations per subject (cluster) was set to 2 (2 eyes per subject) and a correlation between eyes within a subject was set to 0.3 to attain a sample size with a minimum statistical power of 80%.

Secondary Endpoint:

Sample size calculation for the overall CLUE comfort was also performed considering the effect size of 5 (Atlas A -AOA) to achieve a minimum statistical power of 90%. The 2000 trials were simulated for the repeated measurements from the multivariate normal distribution at a 5% significance level using the following covariance attained from the historical data:

Test:

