$u_{11} = 365.99$
 $u_{21} = 214.84$ $u_{22} = 609.18$
 $u_{31} = 176.06$ $u_{32} = 532.54$ $u_{33} = 637.19$
 $u_{41} = 146.71$ $u_{42} = 514.08$ $u_{43} = 590.60$ $u_{44} = 714.34$

Control:

$u_{11} = 429.65$
 $u_{21} = 245.51$ $u_{22} = 590.56$
 $u_{31} = 210.38$ $u_{32} = 520.42$ $u_{33} = 603.15$
 $u_{41} = 254.93$ $u_{42} = 533.15$ $u_{43} = 535.36$ $u_{44} = 643.20$

Table 3: Sample Size Estimations

Endpoints	N per Arm	Power (%)	Total N*
Monocular Visual Acuity 20/40 or better	90	> 90	207
Corneal Staining < Grade 3	116	> 85	270
Acceptable Lens Fit	90	> 90	207
Absolute Rotation within 10-degree	90	> 90	207
Stability with Blink within 5-degree	90	> 90	207
CLUE Comfort	90	> 90	207

*Total N includes ~15% dropout rate

Optimal sample size and its corresponding power for each study endpoint are presented in Table 3. It is determined that a total of 270 subjects (135 per arm) will be sufficient to demonstrate statistical acceptance of both primary and secondary hypotheses.

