5.1. Analysis Specifications

5.1.1. Level of Significance

All planned primary analyses for this study will be conducted with an overall type I error rate of 5%.

The primary analyses (multiple endpoints) will be performed using the intersection-union principal; all primary hypotheses will be simultaneously evaluated using $\alpha = 0.05$. All primary hypotheses must be met in order to claim the success of the study objectives.

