Each eye/subject will be categorized into two groups such that 'response=1' if an eye had acceptable corneal staining (CS) (i.e., CS grade 2 or lower) throughout all planned and unscheduled visits or 'response=0' otherwise. The incidence rate of the Atlas A lens will be compared to the AOA lens using a generalized linear mixed model (Liang and Zeger, 1986²), as implemented in the SAS/STAT procedure GLIMMIX⁷, with binomial distribution and logit link function. The model will include lens type as a

fixed effect and site, subject and eyes nested within subject as random effects. Baseline characteristics such as age and gender may be considered as covariates in the model when appropriate.

The incidence rate of CS for the Atlas A lens will be compared to the AOA lens using the two-sided 95% CI constructed for odds ratios (Atlas A over AOA). No difference between the Atlas A and AOA lenses will be concluded if the 95% CI of the odds ratio contains 1.

In case a full model does not converge for any reasons (likely due to small incidence rate) for any of the primary analyses, a reduced model will be considered.

Additional post-hoc analysis may be conducted if necessary at the discretion of the project leader.

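### The corneal-staining co-primary is met by failing to find a difference, with no margin and no rule for an arm without events

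*SAP*

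**What the plan says.** SAP 5.2.2 fits a binomial-logit mixed model with lens type as fixed effect and forms a two-sided 95% CI for the odds ratio (Test over Control). The decision rule is: "No difference between the Atlas A and AOA lenses will be concluded if the 95% CI of the odds ratio contains 1". Protocol 9.1 agrees: "No difference between Test and Control lenses will be concluded if the 95% CI of the odds ratio contains 1".

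SAP 1.4.1 writes H0: OR = 1 against Ha: OR ≠ 1. In words, however, its alternative is that the odds of unacceptable staining with Atlas A "is not statistically different from the odds of that in the AOA group". It adds a constant that "represents a margin of 1 that reflects distribution similarity between the Atlas A and AOA groups". Protocol 4.1, primary hypothesis 2, asks that the Test lens be no different from Control, or better.

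On consequence, SAP 5.1.1 says: "All primary hypotheses must be met in order to claim the success of the study objectives". SAP 6.1.1 allows secondary testing only after all primaries are met.

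On planning, SAP 1.5 reports no grade 3 or higher staining in five earlier studies, "hence it was deemed that 0.005% is a reasonable incidence rate". It uses two eyes per subject, a between-eye correlation of 0.3 and a minimum power of 80%. Table 3 lists 116 per arm, power above 85% and a total of 270, and the text concludes that "a total of 270 subjects (135 per arm) will be sufficient".

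If the model does not converge, SAP 5.2.2 says "a reduced model will be considered". Protocol 9.1 instead offers Agresti-Coull intervals for binomial proportions. SAP 1.1 gives the SAP precedence over Protocol Section 9.

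**The concern.** The claim the sponsor wants is the null hypothesis, and the rule accepts it whenever the data fail to reject it. The value 1, called a margin in SAP 1.4.1, is the point of no difference and not a tolerance. The 5% alpha then limits only the chance of finding a difference that is not there. Nothing limits the chance of passing a lens that is worse, and a smaller or less informative trial passes more easily.

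The endpoint is also planned to have almost no events. An arm with no events gives no finite odds ratio, so the rule has nothing to act on.

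At stake is a required co-primary that also gates the secondary tests. It could be declared met because events were few, not because similarity was shown.

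**Working it through.** **1. The plan's own figure.** The total is consistent with 116 per arm: 2 × 116 = 232, and 232 × 1.15 = 267 or 232 / 0.85 = 273, against 270 printed. The 116 and the power above 85% cannot be reproduced, because no alternative rate or margin is stated. With two eyes and correlation 0.3 the design factor is (1 + 0.3)/2 = 0.65. Two assumed readings return 116:

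- (i) Power to detect 0.005% v 4.9%, two-sided 5%: 85% at 116 per arm. That is the chance of *failing* this rule.
- (ii) Non-inferiority, 0.5% in both arms, 2-point margin, one-sided 5%: n = 0.65 × 2 × 0.005 × 0.995 × (1.645 + 1.036)² / 0.02² = 116.2 for 85% power. The rule does not test that hypothesis. With 0.005% in place of 0.5% the same formula gives n of about 1.2.

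Reading (ii) suggests the printed rate may be a slip for 0.5%. Only the sponsor can say, so both rates are carried below.

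**2. How often an odds ratio exists.** Inputs: eye rate p, equal in both arms; correlation 0.3 (SAP 1.5); n = 115 per arm (completer target) or 135 (planned randomised).

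P(no affected eye in a subject) = (1 − p)² + 0.3p(1 − p). Raised to the power n, this gives A, the chance that an arm is empty. Both arms are empty with probability A², and at least one with probability 1 − (1 − A)².

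| p | n per arm | A | Both empty | At least one empty |
|---|---|---|---|---|
| 0.005% | 115 | 0.9903 | 98.1% | 99.99% |
| 0.005% | 135 | 0.9886 | 97.7% | 99.99% |
| 0.5% | 115 | 0.3754 | 14.1% | 61.0% |
| 0.5% | 135 | 0.3166 | 10.0% | 53.3% |

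Expected affected eyes per arm are 2np: 0.0115 to 0.0135 at 0.005%, and 1.15 to 1.35 at 0.5%.

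**3. The fallbacks.** Dropping random effects does not remove the empty cell, so a reduced model has the same problem. Agresti-Coull intervals exist at zero events, but they describe one proportion at a time and no comparative criterion is attached. The SAP also supersedes that text.

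**4. What the rule would do (illustration).** The planned GLIMMIX fit was not reproduced; these are stand-ins.

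- Fisher test on eyes, 230 per arm: 5 v 0 affected eyes gives p = 0.061 (pass) and 6 v 0 gives p = 0.030 (fail).
- Plain logistic Wald interval on eyes: with no Control event it contained 1 at every Test count tried, up to 60 eyes, because the standard error of the log odds ratio is about 13,000. With one Control event it excludes 1 from 8 Test eyes: log OR = ln(8 × 229 / 222) = 2.11, SE = √(1/8 + 1/222 + 1 + 1/229) = 1.065, lower limit 0.02. So 60 v 0 passes and 8 v 1 fails.
- Less information helps. By Fisher with independent eyes, at true rates of 2% v 0.005%, the pass rate is 99.9% with 60 eyes per arm, 68% with 232 and 55% with 270.

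Pass rates with Control at 0.005%, 115 to 135 per arm, correlation 0.3:

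| True Test rate | Plain Wald, empty arm counted as pass | Eye-level Fisher to Wald with 0.5 added, variance × 1.3 | Subject-level likelihood ratio |
|---|---|---|---|
| 1% | 99.99% | 92-100% | 60-69% |
| 2% | 99.8-99.9% | 55-99% | 17-26% |
| 3% | 99.4-99.7% | 22-93% | 3-7% |

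With Control at 0.5%, the plain Wald column becomes 99%, 92-96% and 74-84%.

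**5. Direction.** A CI lying wholly on the favourable side of 1 fails the printed rule, although Protocol hypothesis 2 would count that result as success. This is minor, since it is unlikely at these rates.

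**The case against.** The authors foresaw sparse events: both documents mention non-convergence from a small incidence rate. Zero against zero is the expected and benign outcome, so the 99.99% figure is not an error rate. It assumes equal rates in both arms and a printed rate that may be a slip. The pass rates differ widely by interval (3% to 99.7% at a true Test rate of 3%), and none comes from the planned model. Staining is analysed on the safety set, so values near 135 per arm are more relevant than 115. Harm would also still surface through adverse-event reporting.

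Much of this is fair, and it limits what the numbers can show. The pass rates do not measure how lenient the planned analysis is. They show that the verdict depends on an interval method the plan has not fixed for empty arms. The 99.99% shows that the estimand is unavailable, not that a bad lens passes. Foreseeing non-convergence does not help when neither fallback ends in a decision.

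The safety point holds with a qualification. Protocol 8.3 lists other grade 3 or higher corneal findings as significant adverse events, but does not name staining. Protocol 8.4 gives 24 hours for significant events, while 8.2 gives 2 days for all non-serious ones; those passages must be reconciled. The damage is mainly to the formal claim, not to the detection of harm.

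None of this touches the core: success is non-rejection, and there is no margin.

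**Conclusion.** The concern holds, and the rule must be corrected. That success means non-rejection of OR = 1 with no margin follows from the text alone and needs no assumption about rates. The second fault, no decision rule when an arm is empty, applies in 99.99% of trials at the printed 0.005% and in 53-61% if 0.5% was meant. Those figures assume equal rates in the two arms, correlation 0.3 and 115 to 135 subjects per arm. The stated power above 85% cannot be verified, and this row sets the total of 270. The illustrative pass rates are secondary and the conclusion does not rest on them.

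**What to change.** Replace the rule with one-sided non-inferiority of Test to Control on grade 3 or higher staining, the form the SAP already uses for VA 20/20 and CLUE comfort. For example:

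- **Hypotheses (SAP 1.4.1):** H0: p_Test − p_Control ≥ margin; Ha: p_Test − p_Control < margin, where p is the proportion of subjects with at least one affected eye.
- **Decision (SAP 5.2.2, Protocol 9.1):** conclude non-inferiority if the upper limit of the two-sided 95% CI is below a pre-specified margin that the sponsor justifies. A better lens then also passes.
- **Interval:** name one that is defined at zero events, such as Newcombe, score or exact.
- **Unit:** the subject is suggested because the between-eye correlation cannot be estimated with no events. An eye-level interval with the correlation fixed at 0.3 is a possible alternative.
- **Coding:** SAP 5.2.2 codes acceptable staining as 1, while SAP 1.4.1 concerns unacceptable staining. A one-sided rule needs one stated direction.
- **Sample size (SAP 1.5, Protocol 9.2):** confirm 0.005% or 0.5%, and restate the row with rate, margin and resulting power. Neither back-solved reading above should become the margin without justification. Align Protocol 4.1.

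The cost is wording, a margin to justify and possibly less favourable power. With 0 v 0 subjects the Newcombe upper limit is 3.84/(n + 3.84): 3.2 points at 115 per arm and 2.8 at 135, so only larger margins are attainable. Subject-level power at 115 / 135 per arm, for illustrative margins only:

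| True eye rate, both arms | 3 points | 4 points | 5 points |
|---|---|---|---|
| 0.1% (illustrative) | 15% / 80% | 85% / 83% | 98% / 98% |
| 0.5% | 26% / 44% | 62% / 64% | 79% / 85% |

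At 0.005%, a 4-point margin is met essentially whenever the Test arm has no event, so power is about A, or 99%. At 0.5%, of these margins only 5 points with 135 per arm reaches the planned 80% minimum, so the sample size may need review.

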The Kenward and Roger method (Kenward and Roger, 1997) will be used for the calculation of the denominator degree of freedom for the all above statistical models if applicable. If a spatial power covariance structure is selected, the first order option will be used.

In case the statistical model does not converge for any reasons (likely due to small incidence rate) for any of the primary analyses, the 95% CI for the binomial proportions will be constructed using the Agresti-Coull method.

Additional post-hoc analysis may be conducted if necessary at the discretion of the project leader.

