1. INTRODUCTION

1.1. Background

This document describes the data analysis specifications for the protocol CR5871 titled “Evaluation of Astigmatic Contact Lenses”. The test lens is the Johnson & Johnson Vision (JJV) investigational contact lens Atlas A and the control lens is the Alcon Air Optix for Astigmatism® (AOA) which is currently marketed as a monthly replacement.

This Statistical Analysis Plan (SAP) will serve as the final guidance for all the statistical analyses for this study and will supersede the Section 9 in the protocol if there are any discrepancies.

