5.2.2. Analysis Methods

Monocular Visual Acuity (VA) 20/40 or better Analysis

Each eye/subject will be categorized into two groups such that 'response=1' if VA was 20/40 or better (refer as 'acceptable VA') throughout all planned visits or 'response=0' otherwise. The generalized linear mixed model (Liang and Zeger, 1986²), as implemented in the SAS/STAT procedure GLIMMIX⁷, will be

used to assess the overall acceptable VA for each lens type utilizing binomial distribution with logit link function. The model will include lens type as a fixed effect and site, subject and eye nested within subject as random effects. Baseline characteristics such as age and gender may be also included in the model as covariates if appropriate.

The model based proportion of eyes with acceptable VA with its corresponding 95% confidence interval (CI) will be constructed for each lens type from the generalized linear mixed model. Overall acceptable VA will be concluded if the lower limit of the 95% CI is greater than or equal to 0.80 (80%).

Lens Fit Acceptance Analysis

Lens fit acceptance at fitting (Visit 1) will be evaluated by lens type if at least 80% of eyes have acceptable lens fit (response=1) using the generalized linear mixed model (Liang and Zeger, 1986²), as implemented in the SAS/STAT procedure GLIMMIX⁷, with binomial distribution and logit link function. The model will include lens type as a fixed effect and site, subject and eye nested within subject as random effects. Baseline characteristics such as age and gender may be also included in the model as covariates if appropriate.

The model based proportion of eyes with acceptable lens fit with its corresponding 95% CI will be constructed for each lens type from the generalized linear mixed model. Acceptable lens fit will be concluded if the lower limit of the 95% CI is greater than or equal to 0.80 (80%).

Lens Stability with Blink Analysis

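### For the three 80%-threshold co-primaries with a 100% historical rate, the SAP leaves open which interval decides if no Test eye fails; a Wald interval could fail a flawless result, and the stated fallback does not cure this

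*SAP*

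**What the plan says.** SAP 5.2.2 tests four co-primaries against 80%: VA 20/40, lens fit, blink stability and absolute rotation. Each uses a GLIMMIX model with binomial distribution and logit link, lens type fixed, and site, subject and eye within subject random. An endpoint passes if the lower limit of the model-based 95% CI for the Test proportion is 0.80 or more. The interval type is not stated. SAP 6.2.2 applies Kenward-Roger degrees of freedom to all the models where applicable.

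SAP 1.5, Table 2, gives a historical Test rate of 100% for VA 20/40, lens fit and blink stability, and 97% for absolute rotation. For planning, "The common reference rate of 95% was selected for the sample size calculation as all applicable primary endpoints are binary in nature", and the simulation was run "Assuming a correlation of 0.8 between eyes".

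The two documents give different fallbacks for non-convergence, and both expect a small incidence rate to be the likely cause:

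- SAP 5.2.2: "for any of the primary analyses, a reduced model will be considered". No terms, interval or decision rule follow.
- Protocol 9.1: "the 95% CI for the binomial proportions will be constructed using the Agresti-Coull method".

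SAP 1.1 states that the SAP "will supersede the Section 9 in the protocol if there are any discrepancies". The SAP does not mention Agresti-Coull. Under SAP 5.1.1 all primary hypotheses must be met, and under SAP 6.1.1 the secondary tests run only if they are.

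**The concern.** On the sponsor's own history, a Test arm without a single failing eye is a realistic result for three endpoints. A logit model has no finite estimate for an arm with 100% success, so the planned interval may be meaningless exactly when the lens performs best. A reduced logit model has the same problem, because the separation lies in the lens-type estimate and not in the random effects. Both fallbacks are triggered only by non-convergence, and a degenerate fit can report that it converged.

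Since every primary must pass, one such endpoint could fail the study on a literal reading and close the gate to the secondary tests. Otherwise the deciding interval would be chosen after the data are seen.

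**Working it through.** **Inputs.** Rule: lower limit at least 0.80 (SAP 5.2.2). Planning rate 95% and between-eye correlation rho = 0.8 (SAP 1.5). 115 completing subjects per arm, 230 eyes (SAP 1.3); 135 randomised per arm (SAP 1.5). True rates of 99%, 99.5% and 99.9% are assumptions, since the documents give only 100% (historical) and 95% (planning).

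**1. The plan's own figure.** SAP Table 3 gives 90 per arm, power above 90%, total 207. Simulating paired eyes at 95% and rho 0.8 with 90 subjects gives power between 99.2% and 99.99%, depending on the interval. This agrees with the plan, and 180 × 1.15 = 207. A flawless arm of 90 has probability 0.4% at the 95% rate, so the planning simulation hardly meets the case at issue.

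**2. Chance of a flawless Test arm.** With m subjects and true rate p,

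P(no failing eye) = [p(1 − (1 − p)(1 − rho))]^m.

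Example: p = 0.99, rho = 0.8, m = 115 gives (0.99 × 0.998)^115 = 0.98802^115 = 0.25.

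| True rate | m = 115, rho 0.8 | m = 135, rho 0.8 | m = 115, rho 0.3 |
|---|---|---|---|
| 99% | 25% | 20% | 14% |
| 99.5% | 50% | 44% | 38% |
| 99.9% | 87% | 85% | 82% |

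At 95%, with m = 115 and rho 0.8, the chance is 0.09%.

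**3. The stated model at a flawless result.** The site, subject and eye effects were integrated by quadrature, with 115 subjects per arm, 10 sites (assumed), fixed SDs, a fixed Control intercept, and 0 or 3 failing Control eyes. The log-likelihood rose strictly in the Test intercept from 4 to 25 in 8 of 8 settings, so there is no finite maximum.

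**4. A Wald limit along that path.** Ignoring the random effects, with n = 230 eyes and logit η, the limit on the logit scale is η − 1.96/√(n·p(1 − p)). Back-transformed it is 0.968 at η = 5, falls below 0.80 at η = 7.8, and is 0.0001 at η = 10.

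**5. A fixed-effects reduced model.** These fits use 227/230 successes in the Control arm and were made outside GLIMMIX.

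| Test eyes | Interval | Reported convergence | Lower limit | Rule |
|---|---|---|---|---|
| 230/230 | Wald | yes (estimate 25.6, SE about 14,000) | 0 | fail |
| 229/230 | Wald | yes (logit ln 229 = 5.434, SE 1.002) | 0.970 | pass |
| 230/230 | GEE, sandwich SE | yes (SE 0.09) | near 1 | pass |

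The same flawless data pass or fail according to a choice that the SAP does not make.

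**6. Agresti-Coull.** Effective n = 230/(1 + 0.8) = 127.8. Add z² = 3.84 to n and z²/2 = 1.92 to the successes. The adjusted proportion is (127.8 + 1.92)/(127.8 + 3.84) = 0.985, and the lower limit is 0.985 − 1.96·√(0.985 × 0.015/131.6) = 0.965. On 230 eyes treated as independent it is 0.980. With rho fixed at 0.8 the limit is 0.804 at 29 failing eyes of 230 and 0.799 at 30.

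**7. False passes and power with rho fixed at 0.8.** At a true 80% rate and correlation 0.8, the no-failure trigger fires with probability [0.80 × (1 − 0.20 × 0.20)]^115 = 0.768^115, about 7 × 10⁻¹⁴. If the interval alone decided (115 subjects), exact enumeration of eye pairs gives the probability of 29 or fewer failing eyes at a true 80% rate as 0.6%, 1.0% and 1.7% at true correlations of 0.3, 0.5 and 0.8, all below the nominal 2.5%. At 95%, correlation 0.8 and 90 subjects, the interval alone passes with probability 99.7%.

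**The case against.** The strongest reply is that the failure is conditional. The SAP names neither a Wald interval nor an estimation method, and a sandwich-based interval passes. GLIMMIX was not run, so its report on such data is not known. This stands, and it limits the point to what can happen. A reader might infer that the plan will fail a flawless lens; the documents do not support that. They also do not exclude it: a model-based CI with Kenward-Roger degrees of freedom suggests Wald-type limits.

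A second reply is that the protocol already supplies the answer. The SAP overrides protocol Section 9 only where the two differ, and a reduced model that is to be considered could still be followed by Agresti-Coull. So it would be too strong to say that Agresti-Coull has been withdrawn; its status is unclear. Even if it survives, its trigger is non-convergence, and it would not fire when a degenerate fit reports convergence.

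Third, the stakes are modest. Any sensible binomial interval passes at zero failures, and protocol 9.6 requires changes of method to be documented and justified. This also stands. The realistic harm is a method chosen after the data are seen.

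Fourth, the 25% to 87% figures depend on assumed rates, and the documents give no historical sample sizes to bound them. That is correct. The 100% history makes high rates plausible, and for VA the protocol's 20/30 requirement for continuing should make failures of 20/40 rare.

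**Conclusion.** The point holds as a gap in pre-specification for VA 20/40, lens fit and blink stability. At a flawless Test result the stated logit model has no finite estimate, the reduced model does not cure this, and the 0.80 decision depends on an interval that the SAP does not name. With Wald limits, 230/230 can fail where 229/230 passes. The chance of meeting this case ranges from 0.09% per endpoint at the 95% planning rate to 87% at an assumed 99.9% (115 subjects, correlation 0.8).

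A reader might also infer a risk of wrongly accepting a lens. There is none here: the problem arises only when no Test eye fails, and Agresti-Coull then clears 0.80 easily. Absolute rotation, at 97% historically, is much less exposed: 1.5% at a true 97% rate (115 subjects, correlation 0.8). This should be fixed, but it does not undermine the design.

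**What to change.** In SAP 5.2.2, keep the mixed model as the main analysis. For the endpoints with the 0.80 rule, replace the reduced-model sentence with:

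> If no Test eye fails, or if the model does not converge, the 0.80 decision uses the two-sided 95% Agresti-Coull interval (protocol Section 9.1) on the proportion of Test eyes, with effective sample size eyes/(1 + rho) and rho fixed at the planning value of 0.8.

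The first condition covers a degenerate fit that reports convergence. Fixing rho avoids estimating a correlation from few or no failures. The reference to the protocol settles the status of its Agresti-Coull step.

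The cost is one SAP paragraph and a few lines of code, with no extra data or subjects. The interval is slightly wider than one treating eyes as independent (lower limit 0.965 against 0.980 at 230/230), with no material loss of power.

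This interval cannot supply the corneal-staining odds ratio. That endpoint needs its own zero-event rule: at the plan's rate of 0.005% and correlation 0.3, the chance of no event in either arm of 116 is 98.0%.
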